14.2 Clinical Laboratory Variables

Due to COVID-19 PHE related disruptions, it is possible that some test results may be collected from a local laboratory. Local laboratory results and the associated normal ranges will be converted to SI units; local laboratory results, in SI units, will then be normalized to central lab ranges to be included in summary data analysis together with the central laboratory results. The normalization will be performed using the following scale transformation equation:

$$s = L_s + (x - L_x) \frac{U_s - L_s}{U_x - L_x}$$

where s is the normalized individual laboratory value to be used for summary; x is the original value from the local lab; L_x and U_x are the lower and upper limits from the local lab; L_s and U_s are the lower and upper limits from the central lab.

For labs with only a single upper (or lower) limit, the following scale transformation equation will be used:

$$s = x \frac{U_s}{U_x}$$

where s is the normalized individual laboratory value to be used for summary; x is the original value from the local lab; U_s is the upper (or lower) limit from the central lab; U_x is the upper (or lower) limit from the local laboratory. Local laboratory results and normalized results will be included in data listings. Only central lab and normalized local lab results will be used for summary of change from baseline, shift, and potentially clinically important (PCI) analyses.

Clinical laboratory assessments are performed at Baseline, Week 2, Week 12, Week 26 and Week 40/EOT.

- Clinical chemistry serum tests include the following:

- Sodium (Na), potassium (K), chloride (Cl), phosphorus (P), calcium (Ca), carbon dioxide (CO₂), blood urea nitrogen (BUN), creatinine (CR), uric acid
- Alanine aminotransferase (ALT), aspartate aminotransferase (AST), gamma-glutamyl transpeptidase (GGT), alkaline phosphatase (ALP), total bilirubin (TBIL), lactate dehydrogenase (LDH)
- Glucose
- Albumin (ALB), total protein
- Thyroid stimulating hormone (TSH), free T3, and free T4
 - Thyroid Function tests will be performed at Visit 1 (Baseline) and Visit 5
- Pregnancy test
 - A serum pregnancy test will be performed at all designated visits for subjects of childbearing potential
- Hematology tests include the following:
 - Complete blood count (CBC) including:
 - White blood cell (WBC) count
 - Complete differential (relative and absolute)
 - Hematocrit (Hct), hemoglobin, red blood cells (RBC), platelets
 - Reticulocyte count
- Urinalysis tests include the following:
 - Blood, RBCs, WBCs, protein, glucose, ketones, specific gravity, pH

Clinical laboratory values (in Système International [SI] units) and the change from Baseline values will be summarized at each post-Baseline visit using descriptive statistics. The overall minimum, maximum as well as the last post-Baseline observed and change from Baseline values will also be summarized. For urinalysis with categorical results, the number and percentage of subjects will be tabulated by category at Baseline and each post-Baseline visit, and the denominator is the number of subjects with non-missing values for the given parameter and visit.

Laboratory values will also be summarized in shift tables to determine the number and percentage of subjects with values classified as below, within, and above normal ranges at each post-Baseline visit relative to the same classification at the Baseline visit. For the by-visit shift summary, the denominator is the number of subjects with non-missing values at Baseline and the given visit for the given parameter. For the shift to the overall post-Baseline minimum or

maximum, all post-Baseline values will be considered, including unscheduled and out of window values and the denominator is the number of subjects with non-missing Baseline value and at least 1 post-Baseline value for the given parameter.

Clinical laboratory values are potentially clinically important (PCI) if they meet either the low or high PCI criteria listed in [Tables 5](#) and [6](#). The number and percentage of subjects with post-Baseline PCI values for each of the categories in Table 5 and 6 will be summarized for selected parameters. For the overall post-Baseline summaries of PCI values, all post-Baseline values will be considered, including unscheduled and out of window values. Subjects with multiple PCI values for a given parameter will be counted only once for that parameter. For the overall post-Baseline summary, the numerator of the percentage is the number of subjects with at least 1 post-Baseline PCI laboratory value for the given parameter, and the denominator is the number of subjects with at least 1 post-Baseline laboratory value for the given parameter.

Table 5 Criteria for Potentially Clinically Important Laboratory Values – Hematology and Chemistry

| Analyte | Conventional Unit | Low PCI Criteria | High PCI Criteria | SI Unit | Low PCI Criteria | High PCI Criteria |
|------------------------------------|-----------------------|------------------|-------------------|----------------------|------------------|-------------------|
| Hematology (whole blood) | | | | | | |
| Hemoglobin (female) | g/dL | <10 | >17 | g/L | <100 | >170 |
| Hematocrit (female) | % | <30 | >50 | L/L | <0.3 | >0.5 |
| Leukocyte (White Blood Cell Count) | x 10 ³ /uL | ≤2.8 | ≥15 | x 10 ⁹ /L | ≤2.8 | ≥15 |
| Neutrophils | x 10 ³ /uL | ≤1.5 | No upper limit | x 10 ⁹ /L | ≤1.5 | No upper limit |
| Platelet Count | x 10 ³ /uL | ≤75 | ≥700 | x 10 ⁹ /L | ≤75 | ≥700 |
| Chemistry (serum or plasma) | | | | | | |
| ALT | U/L | No lower limit | ≥3 X ULN | U/L | No lower limit | ≥3 X ULN |
| AST | U/L | No lower limit | ≥3 X ULN | U/L | No lower limit | ≥3 X ULN |
| Total Bilirubin | mg/dL | No lower limit | ≥1.5 ULN | umol/L | No lower limit | ≥1.5 ULN |
| BUN | mg/dL | No lower limit | ≥30.0 | mmol/L | No lower limit | ≥10.71 |
| Sodium | mEq/L | ≤125 | ≥155 | mmol/L | ≤125 | ≥155 |
| Potassium | mEq/L | ≤3.0 | ≥5.5 | mmol/L | ≤3.0 | ≥5.5 |
| Calcium, total | mg/dL | <8.0 | >11.0 | mmol/L | <2.0 | >2.75 |
| Lactate Dehydrogenase (LDH) | U/L | No lower limit | ≥3 X ULN | U/L | No lower limit | ≥3 X ULN |
| Alkaline Phosphatase | U/L | No lower limit | ≥3 X ULN | U/L | No lower limit | ≥3 X ULN |
| Uric acid (female) | mg/dL | No lower limit | ≥8.5 | umol/L | No lower limit | ≥505.75 |
| Albumin | g/dL | ≤2.6 | ≥6.0 | g/L | ≤26 | ≥60 |
| Total Protein | g/dL | ≤5.0 | ≥10.0 | g/L | ≤50 | ≥100 |
| Chloride | mEq/L | ≤85 | ≥120 | mmol/L | ≤85 | ≥120 |
| Glucose (random) | mg/dL | ≤45.1 | ≥200.0 | mmol/L | ≤2.48 | ≥11 |
| Serum Creatinine | mg/dL | Not Applicable | >1.5 ULN | umol/L | Not Applicable | >1.5 ULN |
| Gamma-Glutamyl Transferase (GGT) | U/L | Not Applicable | ≥3 ULN | U/L | Not Applicable | ≥3 ULN |

Table 6 Criteria for Potentially Clinically Important Laboratory Values - Urinalysis

| Urinalysis (qualitative dipstick) | Low PCI Criteria | High PCI Criteria |
|-----------------------------------|------------------|-------------------|
| Blood (occult blood) | Not Applicable | \geq Moderate |
| Protein | Not Applicable | ≥ 100 mg/dL |
| Glucose | Not Applicable | ≥ 500 mg/dL |

Clinical laboratory data will be displayed in data listings with date and study day of collection. All units will be displayed according to SI conventions for units. Out of range values will be flagged in the data listings (i.e., 'L' or 'H'). A separate listing will be provided for a subset of the chemistry, hematology, and urinalysis analytes with values classified as PCI.

At the initiation of the study, the main reference ranges (the reference ranges provided by the central laboratory validated for use for the general population) were used for the purpose of flagging abnormal laboratory values for the investigator to assess clinical significance. During the study, at the request of a leading investigator an alternative set of reference ranges, more specific to patients with Rett syndrome rather than to the general population, was used for the purpose of flagging abnormal lab values for the investigator to assess clinical significance.

All analysis will be done using the main reference ranges, not the alternative ranges. During the course of the study the main reference ranges were updated by the central laboratory. The latest version of the reference ranges provided by the central laboratory will be used for all analysis; PCI status and categorical labs (Low, Normal, High) and shifts will be derived from the latest version of the main reference range. Both of the reference ranges (main and alternative) and the corresponding categorical assessment will be listed.

The pregnancy results (positive or negative) will be presented in a listing.

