14. SAFETY ANALYSES

All safety analyses will be performed using the Safety Analysis Set. Safety summaries will be summarized using descriptive statistics by treatment group of the antecedent study and overall. For each continuous measure in clinical laboratory variables, vital signs, and electrocardiogram, change from baseline results will be presented in two ways as specified in [Section 5.1](#).

The primary safety endpoints are:

- Treatment-emergent adverse events (TEAEs)
- Serious adverse events (SAEs)
- Withdrawals due to adverse events (AEs)
- Potentially clinically important changes in other safety assessments

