Electrocardiogram variable average values will be considered PCI if they meet the criteria listed in Table 8. The number and percentage of subjects with post-baseline PCI values will be summarized by treatment group at each post-Baseline visit and for overall post-Baseline. For the by-visit summary, the numerator for the percentage is the number of subjects with a post-Baseline PCI ECG for the given parameter, visit and treatment group, and the denominator is the number of subjects with non-missing values for the given parameter, visit and treatment group. For the overall post-Baseline summary, the numerator for the percentage is the number of subjects with at least 1 post-Baseline PCI ECG for the given parameter and treatment group, and the denominator is the number of subjects with at least 1 post-Baseline ECG value for the given parameter and treatment group. A listing of overall and of all subjects with any PCI ECG values will be provided.

Table 8 Criteria for Potentially Clinically Important ECG Values

| ECG Parameter | Unit | High PCI Criteria |
|----------------------------|------|-------------------|
| QRS Interval | msec | ≥ 120 |
| PR Interval | msec | ≥ 220 |
| QTcB | msec | > 500 |
| QTcF | msec | > 500 |
| QTcB: change from baseline | | > 60 msec |
| QTcF: change from baseline | | > 60 msec |

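### Laboratory, urinalysis and some ECG PCI counts carry no Baseline condition, so a primary endpoint defined as a change may include findings already present before the first dose

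*SAP*

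**What the plan says.** Protocol 2.1.1 and SAP 14 name the same primary endpoint: "Potentially clinically important changes in other safety assessments". The SAP turns this into counts, domain by domain.

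- **Laboratory and urinalysis (SAP 14.2, Tables 5 and 6).** "Clinical laboratory values are potentially clinically important (PCI) if they meet either the low or high PCI criteria listed in" those two tables. The SAP then fixes who is counted across all visits after Baseline: "the numerator of the percentage is the number of subjects with at least 1 post-Baseline PCI laboratory value for the given parameter". This is divided by everyone who has any result for that analyte after Baseline.
- **ECG (SAP 14.4, Table 8).** The count is built in the same way: "the numerator for the percentage is the number of subjects with at least 1 post-Baseline PCI ECG for the given parameter and treatment group". It is divided by everyone in the group who has any ECG result for that parameter after Baseline. Four of the six rows are limits on the observed value (QRS, PR, QTcB, QTcF). The other two are change criteria, for example "QTcF: change from baseline" of more than 60 msec.
- **Vital signs (SAP 14.3, Table 7).** A blood pressure or pulse value must cross a limit and also move by a set amount from Baseline. Weight uses percentage change alone.

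The laboratory shift tables classify "values classified as below, within, and above normal ranges at each post-Baseline visit relative to the same classification at the Baseline visit". The ECG shift table in SAP 14.4 uses the cardiologist's normal or abnormal reading.

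**The concern.** The endpoint is worded as a change, but the laboratory rule and half of the ECG rule measure presence. A subject above a limit before the first dose and still above it afterwards adds one to the count, exactly like a subject who crosses the limit on treatment. A subject with no Baseline value can be counted too.

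This matters more here than in a controlled trial. There is no concurrent comparator and no hypothesis test (Protocol 9.2), so each subject's own Baseline is the main reference. The eligibility criteria in Protocol 4.1 and 4.2 set no numeric laboratory limit, so Baseline PCI values can enter. SAP 14.2 also reports that a Rett-specific set of reference ranges was introduced for flagging, while PCI status stays on the general-population ranges. That establishes no rate, but it makes pre-existing flags on the ULN-based criteria a realistic possibility.

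Subjects who took trofinetide in ACP-2566-003 raise a further issue. Their Baseline is usually the Week 12/EOT value, taken on drug. A Baseline PCI finding may then itself have begun on trofinetide, and the planned counts show neither when it began nor that it persisted.

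**Working it through.** The plan states no PCI rate, so there is no figure to reproduce. The check has two parts.

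**1. Which criteria can count an unchanged finding?**

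| Criterion | Form | Can a subject already PCI at Baseline be counted? |
|---|---|---|
| Table 5, all 21 analytes | observed value | Yes |
| Table 6, all 3 urinalysis tests | observed value | Yes |
| Table 8: QRS, PR | observed value | Yes |
| Table 8: QTcB > 500 | observed value | Yes; exclusion 7 is set on QTcF, not QTcB |
| Table 8: QTcF > 500 | observed value | No; an average Baseline QTcF above 450 ms is excluded (Protocol 4.2, exclusion 7) and eligibility waivers are not granted (Protocol 10.6) |
| Table 8: QTcB and QTcF change > 60 | change | No |
| Table 7, vital signs and weight | change, alone or with a limit | No |

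All laboratory and urinalysis criteria and 3 of the 6 ECG rows are therefore open.

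**Does another planned summary close the gap?**

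- The laboratory shift tables use below, within and above normal. Take two subjects, one going from 1.2 to 4 x ULN on ALT and the other at 4 x ULN throughout. Both read as above-to-above, but only the first newly meets the limit of 3 x ULN.
- Urinalysis categories are tabulated at Baseline and at each visit, but as separate margins.
- QTcB categories are summarized by visit, and SAP Table 2 lists Baseline as an analysis visit. At most this too gives a Baseline margin.
- The second analysis, against the ACP-2566-003 Baseline (SAP 5.1 and 14), covers change in continuous measures and not PCI status.

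**2. How large could the effect be? (Illustration only.)**

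From the documents: N = 180 (SAP 3.5). Assumed, because the documents give no values:
- *b*, the proportion PCI at Baseline, 1% to 10%;
- *p*, the chance that such a subject has at least one post-Baseline PCI value, 0.5 to 1;
- *i*, the new PCI rate among the others, 1% to 5%;
- every subject has both a Baseline and a post-Baseline value.

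Formulas:
- SAP percentage = *b·p* + (1 − *b*)·*i*
- Emergent percentage = *i*, on a denominator of N(1 − *b*)
- Share not new = *b·p* / [*b·p* + (1 − *b*)·*i*]

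Worked case with *b* = 5%, *p* = 0.8, *i* = 3%. Already PCI at Baseline and counted: 180 × 0.05 × 0.8 = 7.2. New: 171 × 0.03 = 5.13. The SAP percentage is 12.33/180 = 6.85%, against 5.13/171 = 3.0% emergent. The share not new is 7.2/12.33 = 58%.

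| *b* | *p* | *i* | SAP count / 180 | SAP % | New count / denominator | Emergent % | Share not new |
|---|---|---|---|---|---|---|---|
| 1% | 0.5 | 5% | 9.8 | 5.45 | 8.9 / 178.2 | 5.0 | 9% |
| 1% | 0.5 | 3% | 6.2 | 3.47 | 5.3 / 178.2 | 3.0 | 14% |
| 5% | 0.8 | 3% | 12.3 | 6.85 | 5.1 / 171 | 3.0 | 58% |
| 10% | 1.0 | 1% | 19.6 | 10.90 | 1.6 / 162 | 1.0 | 92% |

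The first and last rows are the extremes of the assumed grid. Here, not new means that the criterion was already met at Baseline. Such a subject may still have worsened.

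**The case against.** The case for the SAP as written has real weight.

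- **An inclusive count is cautious.** In a descriptive safety study, a count restricted to subjects without PCI at Baseline would lose a subject who goes from 3 to 10 x ULN and anyone without a Baseline value. It would also lose former-trofinetide subjects whose on-drug Baseline was already abnormal. This stands, and it rules out replacing the all-subjects count.
- **The data can be separated by subject.** SAP 14.2 lists all laboratory data with study day and adds a separate PCI listing. For the ULN-multiple criteria, the shift table's above-normal Baseline row gives an upper bound on Baseline PCI. This also stands. A reader might infer that new and persistent findings cannot be told apart at all, but the listings contradict that. What is missing is a summary rate.
- **Adverse events already separate new from old.** SAP 14.1 removes Day 1 events based on pre-dose findings from the TEAEs. That helps for abnormalities reported as events. PCI changes are a separate primary endpoint, however, and have no matching rule.
- **Table specifications are in a separate document (SAP 1).** Baseline PCI rows may be there. That cannot be checked, and the SAP text does not call for them.

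Two further readings go too far. One is that every ECG PCI count is affected. Half of the Table 8 rows are not, as shown above. The other is that the counts do include unchanged findings and so are inflated. The SAP does not say that Baseline-PCI subjects are included. Their possible inclusion follows from the absence of any exclusion, and no document shows how many there are.

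**Conclusion.** The gap is real but limited. For the Table 5 and Table 6 criteria and for QRS, PR and QTcB above 500 msec, the stated rule may count subjects who met the criterion before dosing, and no stated summary separates them. The SAP is also uneven within one primary endpoint, since vital-sign PCI requires a change from Baseline and laboratory PCI does not.

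The size is unknown. The range of 9% to 92% reflects the assumed inputs and is not an estimate. The true share could be small if few subjects are PCI at Baseline, which is plausible for limits this far from normal. No test or sample-size figure depends on it. The effect is on how the PCI percentages can be interpreted. SAP 14.2 also plans PCI summaries only for selected parameters, so not every open criterion need appear in a table.

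**What to change.** In SAP 14.2 and 14.4, keep the all-subjects post-Baseline PCI count. For each observed-value criterion that is summarized, add:

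1. **A treatment-emergent count.** Numerator: subjects with a post-Baseline PCI value who did not meet that criterion at Baseline. Denominator: subjects with a non-missing, non-PCI Baseline and at least one post-Baseline value. Low and high limits are handled separately.
2. **A Baseline-by-worst-post-Baseline PCI shift**, with categories low PCI, not PCI, high PCI and missing. Subjects already PCI at Baseline, those crossing to the opposite limit and those without a Baseline value then stay visible.

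Repeat both against the ACP-2566-003 Baseline for subjects previously on trofinetide, so that an on-drug Baseline does not hide a finding that began in the antecedent study. The QTcF above 500 row needs the addition only for uniformity, and the two change rows need none.

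The cost is SAP wording and a few extra rows per parameter, using data already planned for collection. The emergent rate has a slightly smaller denominator (171 instead of 180 if 5% were PCI at Baseline). The shift table does not show worsening within the same PCI category, which is left to the change-from-Baseline summaries and listings.

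### The two unit columns for the glucose limits in SAP Table 5 disagree by about 0.9%, and the SAP does not say which column sets the PCI flag

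*SAP*

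**What the plan says.** Table 5 in SAP Section 14.2 lists low and high PCI limits for each analyte, first in conventional units and then in SI units. The glucose row is "Glucose (random) | mg/dL | ≤45.1 | ≥200.0 | mmol/L | ≤2.48 | ≥11". The rule for assigning PCI status is "Clinical laboratory values are potentially clinically important (PCI) if they meet either the low or high PCI criteria listed in" Tables 5 and 6. It does not name a unit column.

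The surrounding text works in SI units:

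- Summaries: "Clinical laboratory values (in Système International [SI] units) and the change from Baseline values will be summarized at each post-Baseline visit using descriptive statistics".
- Local results, before they are normalized: "Local laboratory results and the associated normal ranges will be converted to SI units".
- Data that enter the PCI analysis: "Only central lab and normalized local lab results will be used for summary of change from baseline, shift, and potentially clinically important (PCI) analyses".
- Listings: "All units will be displayed according to SI conventions for units".

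The PCI counts "will be summarized for selected parameters", and those parameters are not named. PCI changes in other safety assessments are one of the four primary endpoints (Protocol Section 2.1.1; SAP Section 14).

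**The concern.** Two columns of one table ought to express one limit. If they do not, the same blood result can be PCI under one column and not under the other, and the assignment rule gives a programmer no basis for choosing. The glucose limits are fixed numbers, not multiples of the upper limit of normal, so the SAP's decision to analyse with the latest central-laboratory reference ranges does not remove the difference. A subject counts once any single post-Baseline value meets a limit, unscheduled values included, so one borderline result can change that subject's status. At stake is the exact count in one row of a descriptive table that serves a primary safety endpoint, and whether an independent programmer would reproduce it.

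**Working it through.** **Inputs.** From SAP Table 5: glucose ≤45.1 and ≥200.0 mg/dL; ≤2.48 and ≥11 mmol/L. Assumed, because the documents give no factor: the molar mass of glucose, 6 × 12.011 + 12 × 1.008 + 6 × 15.999 = 180.156 g/mol, so 1 mmol/L = 18.0156 mg/dL. Range tried: 18.0 to 18.02 mg/dL per mmol/L.

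**Reproducing the table's own figures.** The implied factors are 2.48 / 45.1 = 0.05499 and 11 / 200 = 0.0550. A factor of 0.055 returns both SI limits: 45.1 × 0.055 = 2.4805 and 200 × 0.055 = 11.0. The correct factor is 1 / 18.0156 = 0.0555. Rounding a correct conversion does not give 2.48, because 45.1 mg/dL is 2.50 mmol/L to two decimals.

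**Conversion in both directions.**

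| Limit | Table, mg/dL | Converted to mmol/L (range) | Table, mmol/L | Table SI limit in mg/dL (range) | Difference |
|---|---|---|---|---|---|
| Low | 45.1 | 45.1 / 18.0156 = 2.503 (2.503 to 2.506) | 2.48 | 2.48 × 18.0156 = 44.68 (44.64 to 44.69) | −0.93% |
| High | 200.0 | 200 / 18.0156 = 11.10 (11.10 to 11.11) | 11 | 11 × 18.0156 = 198.17 (198.0 to 198.22) | −0.91% |

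The gap is 45.1 − 44.68 = 0.42 mg/dL at the low end and 200 − 198.17 = 1.83 mg/dL at the high end.

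**Which results are classified differently** (whole mg/dL, converted with 18.0156):

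| Result | mmol/L | Meets mg/dL limit | Meets SI limit |
|---|---|---|---|
| 44 mg/dL | 2.442 | yes | yes |
| 45 mg/dL | 2.498 | yes | no |
| 46 mg/dL | 2.553 | no | no |
| 198 mg/dL | 10.990 | no | no (yes if rounded to 11.0) |
| 199 mg/dL | 11.046 | no | yes |
| 200 mg/dL | 11.101 | yes | yes |

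**Other rows that need a molar conversion.** The BUN row is "BUN | mg/dL | No lower limit | ≥30.0 | mmol/L | No lower limit | ≥10.71", and 30.0 × 0.357 = 10.71. Uric acid: 8.5 × 59.48 = 505.58 against 505.75 in the table, a difference of 0.03%. Calcium: 8.0 × 0.2495 = 1.996 against 2.0, and 11.0 × 0.2495 = 2.7445 against 2.75, about 0.2% each. (These factors are standard conversions and are also not in the documents.) Of these rows, only glucose is off by close to 1%.

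**The case against.** The strongest reply has three parts.

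First, the SAP never says that the SI column sets the flag. The SI sentences concern summaries, conversion of local results, and listings. This stands: use of the SI column is a strong inference, not a stated rule. It also supports the point, because the row offers two different criteria and the text does not choose.

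Second, nothing shows which column was intended. A reader might infer that the SI column is the wrong one, so that low glucose values are missed and high ones falsely flagged. The documents do not support that. If 2.48 and 11 mmol/L are the intended limits, the flags are right and only the mg/dL figures are off. The figures do not settle it either: 2.48 / 0.055 = 45.09, so 45.1 could be a back-conversion from 2.48.

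Third, the effect is very small and partly covered elsewhere. Glucose may not be among the selected parameters. All data are listed (SAP Section 5). Section 14.2 also summarizes visit values, overall extremes and shifts against reference ranges, and flags out-of-range values in the listings; none of this depends on Table 5. Investigators assess clinical significance from reference ranges, so no effect on subject care is shown. No hypothesis is tested (Protocol Section 9.2). All of this stands and limits the importance of the point, but it does not make the columns agree.

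A reader might also infer that glucose is a special safety concern because the drug is related to IGF-1 (Protocol Section 1.2) and IGF-1 and insulin are prohibited (Protocol Section 4.6.1). The protocol gives no reason for the prohibition and reports no glucose signal, so the point does not rest on this.

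**Conclusion.** The inconsistency is real. The two glucose columns in Table 5 differ by about 0.9% at both limits, for every plausible conversion factor, and nothing else in the SAP reconciles them. The likely cause is the factor 0.055 in place of 0.0555; that is an inference from the figures. The two columns disagree over a band of about 0.4 mg/dL at the low end and 1.8 mg/dL at the high end, which is one or two whole mg/dL values at each end depending on rounding. Few subjects are likely to fall there, although the documents give no data from which to estimate a number.

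The differences in classification assume that results in mg/dL are converted with the molar-mass factor. If 0.055 were used on the results as well, the flags would follow the mg/dL column at these two points (45 × 0.055 = 2.475; 199 × 0.055 = 10.945), but the reported SI values would then be about 0.9% low. The finding is a minor table correction. It does not establish that any subject is wrongly classified, and it makes no judgement on which limit is clinically right.

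**What to change.** Make the two glucose columns in SAP Table 5 equivalent. If the mg/dL limits are the intended ones, the SI limits become ≤2.50 and ≥11.1 mmol/L. If the SI limits are intended, the mg/dL limits become ≤44.7 and ≥198.2. The sponsor must say which was meant.

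Add one sentence to Section 14.2 stating which unit column is used for all PCI derivations, and the conversion factor and rounding applied before the comparison. The rounding matters at the edge: with 18.02 mg/dL per mmol/L, 200 mg/dL is 11.0988 mmol/L, which meets a limit of 11.1 only after rounding.

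The cost is two numbers and one sentence. No data collection changes, and any PCI glucose flags already programmed need only be rerun.
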